The primary assessment for a difference between intervention arms for 'frequent tester' rates will be a two-sided Z-test for independent proportions with pooled variance. Confidence intervals (95%) will also be reported for the observed difference between the GC and control arms in 'frequent tester' rates. The same analysis plan described above will be used for the other primary outcomes that as binary (i.e., STI testing, PrEP awareness).

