## 6.0 EVALUATIONS AND MEASURES

### 6.1 Behavioral Evaluations

#### 6.1.1 Pre-intervention (Baseline) Evaluations/Measures

- *Socio-demographic information:* We will include questions on race/ethnicity, educational attainment, employment status, housing status, and history of incarceration, sexual identity, and “outness” to their social network.
- *HIV Testing:* The baseline survey will include questions on HIV testing history.
- *STI Testing:* At baseline, we will assess STI testing history and knowledge about STIs. We will ask participants what STIs they have been tested for, the date of their most recent STI test (if known), and whether a medical provider has ever diagnosed them with an STI.
- *Mechanisms of Change:* We will assess YMSM’s psychosocial correlates predicted to adopt HIV services (i.e., Attitudes, Norms, Self-Efficacy, and Behavioral Intentions to get HIV tested). Integrated Behavioral Model constructs will be assessed with 3 subscales assessing YMSM’s attitudes, social norms, and behavioral intentions that we have used in the past with this population. Each attitude item is measured with three five-

point semantic differential scales (good-bad; worthless-valuable; pleasant-unpleasant). Social norms assess the extent to which participants felt that friends and family believed he should test for HIV on a 1 to 5 scale. Behavioral intentions items assess participants' intention to adopt HIV testing, on a 1 (very unlikely) to 5 (very likely) scale. Self-efficacy to access HIV/STI services and to discuss sexuality-related issues with provider will be ascertained, as well as YMSM's perceived confidence of visiting a testing site or requesting a home kit.

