### 6.1.2 On-study Evaluations/Measures

- *HIV Testing:* Follow-up surveys will repeat the HIV testing questions in each follow-up survey. The HIV testing outcome will be: the proportion of MSM tested for HIV two or more times at least 3 months apart in the 12-month follow-up period (“frequent tester”). As an additional analysis, we will also examine the proportions of participants who receive one HIV test.
  - Among self-reported newly diagnosed HIV+ cases, we will measure their linkage and engagement with appropriate medical care after initial diagnosis using criteria employed in prior ATN protocols with youth. We will define linkage as an HIV-related medical visit within 45 days of referral, and engagement as a second HIV-related medical visit within 16 weeks of initial visit. Onset of ART initiation, self-reported adherence to ART, and viral suppression are exploratory indicators, as we recognize that our follow-up period may not be a sufficient amount of time to see these changes.
- *STI Testing:* The STI testing outcome is defined as the proportion of YMSM tested for STIs at least once in the 12-month follow-up period. We will ask participants what STIs they have been tested for, the anatomic sites where they were tested, the date of their most recent STI test (if known), and whether a medical provider had diagnosed them with an STI. In the follow-up surveys, we will ask participants whether they had been tested for STIs in the past 3 months (for the 1-month follow-up survey, we ask about the past 30 days). If STI testing is reported, we will ask participants to indicate what tests they received, and whether they were diagnosed with an STI by a medical provider.
- *PrEP Use:* At each follow-up assessment, PrEP-eligible HIV-negative YMSM (per CDC guidelines) will be asked whether they have begun using PrEP. We will also ascertain if a provider recommended PrEP and/or were offered a prescription for PrEP.
 

*Site Evaluations:* Across both trial arms, YMSM who report testing in the prior 3 months will complete self-evaluation forms of their testing experiences to assess comfort, quality, and concerns after visiting a site for HIV/STI testing and PrEP prevention services. The assessment form is the same form used by the mystery shoppers. We will use these data to update the WebApp and to send aggregate data of YMSM's satisfaction with services to agencies biannually.

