## 10.2 Power Estimates

10.2.1 The primary outcomes for the proposed trial are HIV-negative and HIV-unknown YMSM's successful uptake of HIV and STI testing willingness (e.g., HIV/STI testing), and PrEP awareness and willingness. For HIV testing, we define power as correctly identifying the difference in the proportion of YMSM who engage in HIV testing 2 or more times at least 3 months apart in the 12-month follow-up period ("frequent tester") in our treatment arm (GC) vs. our attention-control arm. For STI testing, we define it as receiving at least one STI test during the 12-month follow-up period. For proportions (e.g., HIV testing; PrEP awareness), our sample size calculations are based on a two-sample test of proportions using a two-sided significance level of 0.05. In order to have 80% power to compare GC to the attention-control group, we require at least 400 participants to find an absolute difference of 13% in cross-sectional analyses. Assuming within-person correlation of 0.25, we can detect an 8.8% difference. A less favorable within-person correlation of 0.75 allows us to detect an 11.3% difference.

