## 10.3 Statistical Analysis Plan

10.3.1 We will use the general framework of generalized linear mixed models (GLMM) to test for intervention effects over time. Note that some of our outcomes are binary, some count and some continuous traits, and thus need to be treated differently. The general form of the GLMM will be  $g(\mu_{ij}) = \beta_0 i + \beta_{cov} Covariates_{ij} + \beta_{Time} j + \beta_{Trt} Trt_{Armi} + \beta_{Arm \times Time}$ , where  $\beta$  is the mean response corresponding to subject  $i$  at Time  $j$  (baseline and 4 follow-ups), with its appropriate link function (identity for continuous outcome, logit for binary outcome and natural log for count outcomes);  $Trt = 1$  if the  $i$ -th subject is in the intervention group and 0 if the  $i$ -th subject is in the attention-control group. The interaction coefficients are of interest here, measuring the difference in the rate of change in outcome across the two treatment groups over time. The subject-specific random intercepts are assumed to be normally distributed with a common variance and they account for within-person correlation. We will also explore if we need a subject-specific random-slope corresponding to visit in the above model. Maximum likelihood estimation will be used for fixed effect parameters. Models will be compared according to information criterion like AIC, BIC. For some binary outcomes like HIV testing, we will perform an aggregate analysis after collapsing across the repeated measures using simple logistic regression comparing whether the probability of having tested at least once over the entire FU period is different across treatment groups, after adjusting for baseline values. To ensure robustness, we will also apply an exchangeable working correlation structure to its corresponding generalized estimating equation (GEE) model. We will also conduct exploratory regression analyses to examine city differences in the outcomes. These regressions will be run with group assignment and city in the model, controlling for socio-demographic characteristics.

Interactions between group assignment and city will be tested to explore potential site-specific moderators of treatment effect.

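### The primary STI-testing comparison in section 2.4 leaves out the STI-testing history collected at baseline, and section 10.3.1's baseline-adjusted model is not clearly assigned to it; the cost is precision, not validity

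*Combined protocol and SAP*

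**What the plan says.** **Primary analysis.** Section 2.4 (binary outcomes) names a two-sided pooled Z-test as the primary assessment of frequent-tester rates. It also specifies a GEE over the five follow-up surveys with three predictors: arm, time and arm-by-time. It carries both to STI testing: "The same analysis plan described above will be used for the other primary outcomes that as binary (i.e., STI testing, PrEP awareness".

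**Outcome.** Section 6.1.2: "The STI testing outcome is defined as the proportion of YMSM tested for STIs at least once in the 12-month follow-up period". Sections 3.1 and 10.2 also list STI testing among the primary outcomes, while section 2.4 singles out HIV testing as the primary outcome for the trial.

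**Baseline data.** Section 6.1.1: "At baseline, we will assess STI testing history and knowledge about STIs". The survey also takes the date of the latest STI test, where known.

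**Design control.** Sections 4.1 and 4.2 set no condition on past STI testing. The only testing criterion concerns HIV, and it is one side of an and/or rule. Section 5.3 stratifies by city/SRV alone.

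**Other analysis text.** Section 10.1.1 plans regressions of the primary outcomes with arm only, then with demographics, substance use, distress and intervention process data; STI-testing history is not listed. Section 10.3.1 plans a mixed model with a covariate term and baseline among the response times. It also plans a logistic regression of at least one test over follow-up, "after adjusting for baseline values", for some binary outcomes, with HIV testing as its example.

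**The concern.** Men never tested for STIs and men tested last month can both enrol, and only chance balances them between arms. Past testing is a plausible predictor of any STI test in the next 12 months, and the protocol tailors intervention content to testing history (section 3.1). If the predictor is useful, leaving it out keeps removable variance in the test. It also lets a chance excess of habitual testers in one arm move the observed difference.

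At stake is the precision of one of the listed primary outcomes. A second issue is clarity: sections 2.4, 10.1.1 and 10.3.1 describe different analyses for the same outcome, and none says which governs.

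**Working it through.** **Inputs from section 10.2.** The test of two proportions is two-sided at the 5% level. On numbers, the section says: "In order to have 80% power to compare GC to the attention-control group, we require at least 400 participants". The target effect is 13 percentage points, cross-sectionally. Allocation is 1:1 (section 5.3), so 200 per arm.

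**Assumptions, not in the documents.** The control rate; the correlation r between baseline STI-testing history and any STI test in 12 months; and the share with prior STI testing.

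**1. The plan's own figure.** Pooled formula, per arm:

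n = [1.960·√(2p̄(1−p̄)) + 0.842·√(p₀(1−p₀) + p₁(1−p₁))]² / (p₁−p₀)²

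With p₀ = 0.25, p₁ = 0.38 and p̄ = 0.315, this gives 200 per arm, or 400 in total, which matches. Other control rates with a 13-point difference give 360 (20%), 430 (30%) and a maximum of 464 (near 43.5%). The stated 400 is therefore attainable but cannot be confirmed, because no control rate is stated. I use 25% versus 38% below because it returns the plan's figure.

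**2. Effect of adjustment.** Adjusting for a baseline variable with correlation r multiplies the variance by about 1 − r². Total N for equal precision is 400(1 − r²), and power is that of 200/(1 − r²) per arm.

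| r (assumed) | Power | Detectable difference (points) | N for equal precision |
|---|---|---|---|
| 0 (unadjusted) | 80.1% | 13.0 | 400 |
| 0.10 | 80.5% | 12.9 | 396 |
| 0.25 | 82.6% | 12.5 | 375 |
| 0.40 | 86.5% | 11.8 | 336 |
| 0.50 | 90.0% | 11.2 | 300 |

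**3. Simulation check.** 20,000 trials per setting, 200 per arm, with a binary baseline history. The pooled Z-test had about 80% power throughout. A test stratified on history (Cochran-Mantel-Haenszel) had 80.2%, 82.6%, 85.8% and 88.9% at r = 0.10, 0.25, 0.40 and 0.50. Type I error was between 4.8% and 5.1% for both tests.

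**4. Chance imbalance.** Assume half the sample has prior STI testing. The standard deviation of the between-arm difference in that share is √(0.5 × 0.5 × 2/200) = 0.05, so its 95% range is ±1.96 × 5 = ±9.8 points. The difference in outcome rate between men with and without that history is r·√(0.315 × 0.685/0.25) = 0.93r. The 95% range of the resulting shift in the unadjusted difference is ±0.9 points at r = 0.10, ±2.3 at r = 0.25 and ±4.6 at r = 0.50, against a 13-point target.

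**5. Can the covariate be used?** The abstract and section 5.1 place randomization before the baseline survey, and section 5.1 places the survey before WebApp access. Section 3.4 intends participants to be blinded. The answers come after randomization but before exposure to the intervention.

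**The case against.** The strongest reply is that the plan already covers this. A reader of section 2.4 alone might infer that baseline STI testing is used nowhere. The documents do not support that: section 10.3.1 includes baseline among the mixed model's response times and adjusts an at-least-once logistic model for baseline. At-least-once is the form of the STI outcome and not of the frequent-tester outcome, and HIV testing is given there only as an example. This stands as far as it goes, but STI testing is not named, the baseline variable is not defined, and section 2.4 still makes the unadjusted test the primary assessment. Section 10.1.1 does not fill the gap either: it omits STI-testing history, and its process covariates arise after randomization.

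Second, a reader might infer that the unadjusted result is biased or its error rate inflated. It is neither. Randomization makes the Z-test valid, and its standard error already allows for chance imbalance on average.

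Third, r is unknown and may be low. The baseline item is self-reported, with a date only where known, and lifetime history may predict less well than recent testing. Section 10.2's correlations ("Assuming within-person correlation of 0.25, we can detect an 8.8% difference", and 11.3% at 0.75) are not stated to be baseline-to-outcome correlations, so they cannot settle r. This stands, and the low values belong in the range.

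Fourth, HIV testing is the outcome section 2.4 singles out, and the sample size rests on a simple two-proportion test. Both points limit the weight of the concern without removing it.

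**Conclusion.** The point holds as a matter of efficiency and specification. The section 2.4 primary analyses of STI testing do not use a collected baseline variable that the design leaves uncontrolled, and a suitable baseline-adjusted model in section 10.3.1 is neither clearly assigned to STI testing nor made primary.

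The size depends on r, which the documents do not give. From 80.1% unadjusted power, the gain is about 0.4 points at r = 0.10, 2.5 at r = 0.25, 6 at r = 0.40 and 10 at r = 0.50: small up to 0.25, material from 0.40. These figures assume 25% versus 38% and 200 per arm. The documents do not support calling the comparison invalid, biased or underpowered on this ground.

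**What to change.** - **Section 2.4, primary STI-testing comparison.** Use a logistic regression of any STI test in 12 months on arm and a pre-specified baseline STI-testing category, for example never, not recent, recent, or date unknown, with the cut-point fixed in advance. Report a standardised risk difference with 95% CI, which keeps the absolute scale of section 10.2. Keep the pooled Z-test as a supporting analysis.
- **STI-testing GEE.** Add the same category.
- **Section 10.3.1.** Align it: name STI testing and the baseline variable, and state that section 2.4 governs.
- **Timing and missing answers.** State that the baseline survey follows randomization but precedes WebApp access. Keep participants with no baseline answer in the model through a missing/unknown category, so that all randomized participants remain included as section 2.4 requires.

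Cost: wording and slightly more analysis work, with no new data or participants. The downside is that the primary test is no longer identical to the two-proportion test behind the sample size.

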### **Binary outcomes such as HIV testing:**

The percentage of participants who report routine HIV testing over a 12-month period will be compared between the intervention arms (GC and the Control condition). Five assessments will occur at 1 month (visit window  $\pm$  1 month), 3 months ( $\pm$  1 month), 6 months ( $\pm$  1 month), 9 months ( $\pm$  1 month), and 12 months ( $\pm$  1 month). Repeated-measures analyses for HIV testing will be implemented by performing a generalized estimating equations (GEE) analysis via the SAS GENMOD Procedure (version 9.4; SAS Institute, Cary, NC) with an exchangeable correlation structure for the repeated measures within participant (binomial-logit model). The statistical model will include three predictors (intervention arm, time on study and the statistical interaction between intervention arm and time on study). The statistical model will provide estimates of the percentages of participants reporting HIV testing (plus 95% confidence intervals) by intervention arm and time on study. The model-based estimates are unbiased with unbalanced and missing data, so long as the missing data are non-informative (missing completely at random, MCAR). A P value  $\leq 0.05$  will be considered statistically significant for the main effects (intervention and time on study) and for the intervention by time on study interaction effect from the repeated measures analysis. **The statistical test for interaction between time on study and intervention arm will be the primary overall hypothesis test to determine whether HIV testing in the intervention groups changed in significantly different ways during follow-up (i.e., different temporal patterns over time).** If HIV testing rates in the two intervention groups are consistently different or similar (i.e., no statistical interaction) then the main effect test for intervention will be used as the primary test of intervention efficacy. If a significant interaction is detected, then Wald chi-square tests will be used to compare the differences between the model-based HIV testing estimates at each time interval and to compare differences over time within each intervention arm. Specific statistical tests will be done within the framework of the generalized linear model. All statistical tests will be 2-sided and unadjusted for multiple comparisons.

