- Sexual Risk Behavior:* Sexual risk behavior will be assessed using the Sexual Practices Assessment Schedule used in previous online studies with YMSM to explore the number of occasions of different sexual acts (oral, anal; receptive, insertive) with three different types of partners (romantic interest, casual partner “hookup,” or friend with benefits), use of condoms during the past 3 months, and knowledge about partners' HIV status and PrEP use. Assessments ascertain sexual behaviors with male and female partners, and will be asked at each follow-up. At-risk sex will be defined as any anal intercourse without condoms and/or PrEP that occurs with a person of known positive or unknown sero-status. We will assess the number of partners with whom participants had “at-risk sex.”
- PrEP Awareness and Willingness:* The survey will contain a brief description of PrEP to orient the participant. Questions are adapted from recent studies of PrEP attitudes with YMSM. PrEP awareness will be a single item measure of whether the participant has heard of PrEP (yes/no/I don't know). PrEP willingness will be measured with an existing 8-item scale developed for YMSM to gauge likelihood of PrEP use across different conditions (e.g., partner types; experiencing potential side effects).
- Technology and Social Media Use:* Given the online interface of the intervention, we will include Pew Internet Survey questions regarding use of different devices, the number of hours spent online through each device, the reasons for social media use, sites commonly frequented, and extent to which the Internet supplements face-to-face interactions. We will also measure AMSM's frequency of use of social media to look for HIV or sexual health-related information, and their online partner-seeking behaviors

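### The section 2.4 tests of PrEP awareness leave out the baseline answer to the same item; the comparison stays unbiased but loses precision that the baseline survey could supply

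*Combined protocol and SAP*

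**What the plan says.** Section 2.4, under binary outcomes, describes a binomial-logit GEE over the five follow-up visits: "The statistical model will include three predictors (intervention arm, time on study and the statistical interaction between intervention arm and time on study"). The arm-by-time interaction is the primary overall test, and the arm main effect takes over when there is no interaction. A pooled-variance Z-test is added for frequent-tester rates. The plan is then extended: "The same analysis plan described above will be used for the other primary outcomes that as binary (i.e., STI testing, PrEP awareness").

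Section 6.1.1 lists awareness among the baseline measures: "PrEP awareness will be a single item measure of whether the participant has heard of PrEP", answered yes, no or I don't know. Under section 5.1, men are consented, then randomised, then complete the baseline survey, and only after that are helped onto the WebApp.

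Two other sections bear on this:

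- **Section 10.1.1** runs regressions with arm alone and again with covariates (socio-demographics, substance use, distress and process data). Baseline awareness is not listed.
- **Section 10.3.1** sets out a GLMM with a covariate term and with baseline as one of the repeated responses. It adds: "For some binary outcomes like HIV testing, we will perform an aggregate analysis after collapsing across the repeated measures using simple logistic regression". That analysis adjusts for baseline values, and its endpoint is having tested at least once.

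**The concern.** A man who has heard of PrEP at entry will probably say so again later, whichever arm he is in. The baseline answer is therefore likely to explain part of the variation at follow-up. Leaving it out treats that part as noise. The estimate is less precise and power is lower than the collected data allow, on an outcome that the plan calls primary. HIV testing is the lead outcome under section 2.4, so this does not touch the trial's main conclusion.

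Sections 2.4 and 10.3.1 also bring baseline in differently, and neither is named as governing for awareness. If adjustment is not prespecified, adding it after an imbalance has been seen would look data-driven.

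**Working it through.** **1. The plan's own figure.** Section 10.2 uses a "two-sample test of proportions using a two-sided significance level of 0.05" and says "we require at least 400 participants to find an absolute difference of 13% in cross-sectional analyses", at 80% power. The control rate is not stated, so the figure cannot be reproduced from the documents alone. With pooled variance and 1:1 allocation, n per arm = [1.960·√(2p̄(1−p̄)) + 0.842·√(p₀(1−p₀) + p₁(1−p₁))]² / (p₁−p₀)².

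- 25% vs 38%, or 62% vs 75%: 199.2, rounded up to 200 per arm, 400 in total (power 80.1%).
- 43.5% vs 56.5%: 231.03, rounded up to 232 per arm, 464 in total. With 400 men the power is 74.1%.

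So 80% is attainable, but it depends on the control rate. It is taken as the starting point below.

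**2. Gain at a single time point.** Let r be the correlation between baseline and follow-up awareness. Adjustment multiplies the variance by 1 − r², so power = Φ((1.960 + 0.842)/√(1 − r²) − 1.960).

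| Assumed r | 1 − r² | Power from 80% |
|---|---|---|
| 0.3 | 0.91 | 83.6% |
| 0.4 | 0.84 | 86.4% |
| 0.5 | 0.75 | 89.9% |

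At r = 0.5 this is worth 400/0.75 = 533 men. From the less favourable 74.1% start, power becomes 78.0% at r = 0.3 and 85.3% at r = 0.5. Simulated logistic regression with 200 per arm and r = 0.5 moved power from 80.8% to 90.1% (62% vs 75%) and from 82.8% to 90.8% (25% vs 38%).

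**3. What holds the gain down.** Only an assumed r is available. The 0.25 and 0.75 in section 10.2 are generic within-person values, not specific to awareness.

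- *Ceiling.* Section 6.1.1 says the survey describes PrEP to every participant. If awareness rose from 50% to 90%, r could not exceed √(0.5×0.1/(0.9×0.5)) = 0.33, giving about 84%.
- *Low baseline.* With 62% vs 75% at follow-up and 95% of baseline-aware men still aware, simulated power after adjustment is about 83 to 84% when 15 to 20% are aware at baseline. It is about 86% at 30% aware and 89% at 40%.
- *Weaker persistence.* At 40% baseline awareness with 85% still aware, it is about 84%.

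**4. The other tests in section 2.4.** A baseline covariate is constant over time and drops out of within-person contrasts. In two simulated patterns the interaction test had 62.7% power with and without it, and 32.3% with and without it. The five-visit arm main effect moved from 79.5% to 94.6% at r of about 0.5.

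**5. The section 10.3.1 GLMM.** With baseline as a response and a free arm effect, the arm-by-time contrast against baseline compares changes. At a single follow-up its variance relative to the unadjusted comparison is 2(1 − r): 1.4 at r = 0.3, 1.0 at 0.5 and 0.8 at 0.6. The adjusted factor 1 − r² is 0.91, 0.75 and 0.64 at the same values. The difference is (1 − r)², so covariate adjustment is never the less precise of the two.

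**The case against.** The strongest reply is that nothing here is invalid. That stands. Randomisation makes the unadjusted comparison unbiased, and chance imbalance is already covered by the 5% error rate. At an assumed 40% baseline awareness, the SD of the difference between arms in baseline-aware men is √(2×0.4×0.6/200) = 4.9 points. A reader might infer that such an imbalance could pass for an intervention effect, but that is ordinary sampling error.

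Second, a reader might infer that the plan's primary test would rise to 90% power. It would not: section 2.4 puts the interaction first, and that test gains nothing. The gain belongs to the Z-test and to the main effect, which becomes the primary efficacy test only when there is no interaction. The Z-test is itself written for a 12-month frequent-tester rate, and no visit is named for awareness.

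Third, section 10.3.1 does bring baseline in. It would be wrong to say that its GLMM never helps: above r = 0.5 it is more precise than the unadjusted comparison. Its baseline-adjusted logistic analysis is offered for outcomes like HIV testing, which does not strictly exclude others. Still, awareness is not named, and an endpoint of having tested at least once does not fit it.

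Finally, the baseline survey follows randomisation. That is a real caution. However, it precedes WebApp access, and section 3.4 intends participants to be blinded, so the item remains a reasonable covariate.

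**Conclusion.** The point holds as a matter of efficiency. No section clearly prespecifies baseline adjustment for PrEP awareness, although the item is already collected. For a comparison at one time point starting from 80% power, the gain runs from about 4 points at r = 0.3 to about 10 at r = 0.5. A ceiling or low baseline awareness would keep it near the lower end. These sizes rest on an assumed correlation, assumed awareness rates and a control rate that makes the plan's 80% true. There is no bias to correct and no gain for the interaction test. The change is worth making because it costs almost nothing, but it concerns one of several primary outcomes and not the lead one.

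**What to change.** In section 2.4, and consistently in 10.3:

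1. Prespecify baseline awareness (yes vs no/I don't know, with a missing category so that nobody is dropped) as a covariate in the awareness GEE.
2. Report the percentages by arm and time, and the arm difference, standardised over baseline awareness with robust 95% confidence intervals. Without standardisation, the added logit term would turn the marginal odds ratio into a conditional one.
3. Name the visit or summary at which the baseline-adjusted risk difference replaces the Z-test, and keep the unadjusted Z-test as supporting.
4. State that the baseline item is answered after randomisation but before WebApp access.
5. Optionally, treat STI testing the same way. Section 6.1.1 says "At baseline, we will assess STI testing history and knowledge about STIs", but the date of the last test is recorded only where known, and the aggregate analysis in 10.3.1 may already cover this outcome.

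The cost is a few lines of analysis-plan text and one extra model term, with no new data and no more participants.
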